11.5.7 Subset Analysis

Subset analyses within the ONN arm comparing outcomes for subjects receiving navigation services from GI specialist versus general navigation services will be performed. These analyses will be conducted on the primary and secondary endpoints as described above.

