1.1.8 The Role of Oncology Nurse Navigators at LCI

Oncology Nurse Navigators are usually “tumor site-specific”. At LCI GI clinics, they are currently employed to care exclusively for patients with gastrointestinal cancers (GI NN). Regional sites with lower volumes have General Nurse Navigators working with all types of cancers (General NN).

Oncology Nurse Navigators at LCI play many roles such as:

1. Care Coordinator. This encompasses expediting care and facilitating communication between providers, the patient, and the family. LCI Navigators communicate across treatment modalities and expedite referrals. They oversee the coordination of appointments and ensure that they are made in a timely manner.
2. Patient-centered assessor of barriers to care. This includes assisting patients in overcoming the challenges encountered throughout their treatment. These barriers can be logistical, health literacy-related, psychosocial, financial, transportation-related, etc.
3. Patient educator. This involves communicating with the patient to ensure that they understand their disease, their care plan, their treatment, and how to manage their symptoms and treatment side-effects.
4. Patient referral specialist. Referral of patients to appropriate resources helps the patients to overcome identified barriers related to finances, treatment logistics, psychosocial health, transportation, and health literacy, for example. These resources may be within the healthcare system or the community.
5. Patient advocate. Navigators serve as patient advocates and provide a central point of contact for the patient as issues and concerns related to their care arise.

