2.1.3 Exploratory objectives

- To compare outcomes within the ONN arm for subjects navigated by GI specialists versus subjects navigated by general oncology nurse navigators.

- To describe the distribution of the timing from enrollment to initiation of systemic therapy.
- To evaluate outcomes within the ONN arm as a function of the time from enrollment to initiation of systemic therapy in those evaluable subjects initiating systemic therapy on study.

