3. SUBJECT SELECTION

3.1 Subject Identification and Recruitment

Subjects will be recruited at LCI sites where ONN performed under the LCI Patient Navigation Program is available. Patients with the diagnosis of GI cancers (as defined in the inclusion criteria) who are not previously or currently receiving navigation service in LCI will be identified and enrolled into the study. Patients will not be excluded from recruitment based on their gender, race, or ethnic origin.

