4. SUBJECT ALLOCATION

4.1 Randomization

Following informed consent and eligibility check per standard operating procedures, subjects will be randomized in a 1:1 fashion to either Arm A (standard of care plus ONN service) or Arm B (standard of care only) and assigned a Sequence Number. This will be accomplished utilizing the CTMS whereby a list of Sequence Numbers and associated treatment arm assignments randomly generated prior to study activation will be uploaded by a member of the Levine Cancer Institute Data Coordinating Center. The Sequence Number will be a four digit randomly generated ID number, ranging from 0001 to 9999. A stratified block randomization will be utilized including the following stratification factors to reduce confounding of comparisons between the treatment arms:

- COVID-19 study period:
 - Time from study activation to end of pandemic* (Study Period A)
 - End of pandemic to end of study (Study Period B)
 - Note: The time of the start of the post-pandemic era will be determined by a declaration from World Health Organization, Center for Disease Control (or other United States federal agency), or LCI, whichever comes first.

*On January 30, 2023, the Biden Administration announced its plan to end the COVID-19 national emergency and public health emergency in the United States on May 11,

2023. The end of the pandemic will be defined by the United States declaration of the end of the COVID-19 national emergency and public health emergency.

- Disease diagnosis:
 - Metastatic pancreatic
 - Locally advanced unresectable pancreatic
 - Metastatic or unresectable esophageal, gastroesophageal junction (GEJ) or gastric cancers
 - Metastatic or unresectable hepatocellular carcinoma
 - Metastatic or unresectable biliary cancer
 - Colorectal cancer patients who had disease progression on or are intolerance to fluorouracil, oxaliplatin, and irinotecan-based therapy

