5. STUDY PLAN

See Schema (Table 1).

This trial is designed to evaluate the impact of ONN in addition to standard care (compared to standard care alone without ONN) on GI cancer patients' acute care utilization as well as clinical outcomes. Subjects enrolled to this study will be patients presenting to the GI clinic.

Enrollment of patients onto this study will not affect the course of their cancer treatment in any way; however, we hypothesize that those randomized to ONN will have less utilization of acute care and an improved survival compared to those receiving standard care only.

Target accrual period is anticipated to be 48 months.

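### The exploratory GI-specialist versus general navigator comparison is made only inside the ONN arm, where navigator type largely follows the clinic, so a site difference would read as a navigator effect

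*Combined protocol and SAP*

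**What the plan says.** Section 2.1.3 (Exploratory objectives) sets the aim: "To compare outcomes within the ONN arm for subjects navigated by GI specialists versus subjects navigated by general oncology nurse navigators". Section 11.5.7 carries it out: "Subset analyses within the ONN arm comparing outcomes for subjects receiving navigation services from GI specialist versus general navigation services will be performed". It applies this to the primary and secondary endpoints with the methods given earlier in Section 11.5.

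Section 1.1.8 describes where each type of navigator works. On the GI navigators: "At LCI GI clinics, they are currently employed to care exclusively for patients with gastrointestinal cancers (GI NN"). On the general navigators: "Regional sites with lower volumes have General Nurse Navigators working with all types of cancers (General NN").

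Section 3.1 defines the recruiting sites: "Subjects will be recruited at LCI sites where ONN performed under the LCI Patient Navigation Program is available". Section 4.1 allocates individual subjects 1:1 to ONN or control and says "A stratified block randomization will be utilized including the following stratification factors". The factors listed are COVID-19 study period and disease diagnosis. Neither site nor navigator type is among them.

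The modelling part of Section 11.5.5 considers demographic, socioeconomic and clinical baseline factors and does not name site. No section plans an arm-by-site or arm-by-navigator-type analysis, and none notes that navigator type is tied to location.

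Section 5 describes the population differently from Section 3.1: "Subjects enrolled to this study will be patients presenting to the GI clinic".

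**The concern.** Comparing GI-navigated with generally navigated subjects inside one arm is an observational comparison. The two groups differ in the nurse, but also in most things that go with the place of treatment: case mix, travel distance, clinic volume, and local access to emergency and urgent care. The last of these bears directly on ACU. The planned contrast cannot separate the nurse from the place.

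The protocol gives reasons to take this seriously. Section 1.2 justifies the trial because earlier navigation results might reflect case selection despite propensity matching. Section 1.1.3 cites geographic location as a correlate of survival after pancreatic resection. Section 1.1.1 mentions variation in survival between hospitals.

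The control arm holds relevant information that the plan does not use. If regional sites enrol and individuals are randomised there, their control subjects show how those sites do without navigation. At stake is how one exploratory result is read, not the trial's main conclusion.

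**Working it through.** The plan gives no sample size, power, alpha or expected split for this comparison, so there is no figure of its own to reproduce. The check asks what the planned contrast shows when navigator type has no effect.

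**Inputs from the documents.** 150 evaluable subjects per arm (Section 11.5.8). Control OS6 of about 60%, 6 acute care visits per year in the control arm, and a 20% reduction (Section 11.2), so 6 × 0.8 = 4.8 visits per year under navigation.

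**Assumed.**
- A share s of 50%, 70% or 80% of each arm is at GI-navigator sites.
- The baseline OS6 difference d between site types is 0 to 20 points.
- Navigation adds 10 points at both site types.
- Subset tests are two-sided at 0.05, with normal approximations.
- For ACU, follow-up is 0.5 or 1 year, with Poisson variance and no overdispersion.

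**OS6, expected values.** Control rates are p_G = 0.60 + d(1 − s) at GI-navigator sites and p_R = 0.60 − d·s at general-navigator sites, which average 0.60.
- Within-ONN contrast: (p_G + 0.10) − (p_R + 0.10) = d. The whole site difference is shown as a navigator difference.
- Arm-by-site-type interaction: [(p_G + 0.10) − p_G] − [(p_R + 0.10) − p_R] = 0.

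**One case in full: s = 70%, d = 0.10.** The ONN rates are 0.73 (n = 105) and 0.63 (n = 45).
- SE of the within-ONN contrast = √(0.73×0.27/105 + 0.63×0.37/45) = 0.084.
- 0.10/0.084 = 1.19, so P(significant) = Φ(1.19 − 1.96) + Φ(−1.19 − 1.96) = 0.22.
- The controls, at 0.63 and 0.53, add 0.63×0.37/105 + 0.53×0.47/45 to the variance. The interaction SE is 0.122 and its 95% half-width is 1.96 × 0.122 = 0.239.

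**Probability that the within-ONN OS6 contrast is significant, with no navigator-type effect**

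| Baseline gap d | s = 50% (75/75) | s = 70% (105/45) | s = 80% (120/30) |
|---|---|---|---|
| 0 | 0.050 | 0.050 | 0.050 |
| 5 points | 0.103 | 0.092 | 0.082 |
| 10 points | 0.270 | 0.222 | 0.176 |
| 15 points | 0.529 | 0.426 | 0.330 |
| 20 points | 0.782 | 0.654 | 0.521 |

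Over this grid the within-ONN SE is 0.073-0.099 and the interaction SE is 0.107-0.142, about 1.4 to 1.5 times as large. The interaction's 95% half-width is 21 to 28 points.

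**ACU.** Let R be the visit rate at general-navigator sites divided by that at GI-navigator sites. The within-ONN log rate ratio has expectation log R. Its SE is √(1/(n_G·4.8·t) + 1/(n_R·4.8R·t)). For s = 70%, R = 1.2 and t = 1, the SE is √(1/504 + 1/259.2) = 0.076. Then log 1.2 = 0.182, and P(significant) = 0.665. Over all splits and both follow-up times the range is 0.117-0.258 for R = 1.1 and 0.318-0.724 for R = 1.2. The interaction compares 4.8/6 with 4.8R/(6R). Both equal 0.8, so the ratio of rate ratios is 1.

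**Scale.** The interaction is zero only on the scale on which the navigation effect is constant. Moving from 60% to 80% is an odds ratio of (0.8/0.2)/(0.6/0.4) = 2.67. Applied to a 70% baseline, the odds are 2.333 × 2.667 = 6.22, or 86%. The effects are then 16 and 20 points, an interaction of about −4 points on the risk-difference scale with none on the odds scale. The scale must therefore be named in advance.

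**The case against.** The strongest reply is that this is an exploratory subset analysis with no alpha, power or decision rule, and that a sentence calling it non-randomised would meet most of the point. That stands as to weight. It does not make the contrast informative about navigators, and the plan contains no such sentence.

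Second, the link between navigator type and clinic is not perfect. Section 1.1.8 says navigators are usually tumour-site-specific and describes current staffing. Section 5.1 allows telephone and virtual contact, and Section 8.3 allows moves between LCI sites. This too stands: classification by enrolling site will sometimes differ from the navigator actually met.

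Third, Section 11.5.7 may bring in the adjusted models of Section 11.5.5, and zip code, income and insurance are collected. Adjustment could remove part of a case-mix or distance difference. It cannot remove an effect of the site itself, and a site term within the ONN arm would be nearly collinear with navigator type.

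Fourth, the site differences are assumed. No section gives one, and at 5 points the false-positive rate rises only from 5% to 8-10%.

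Finally, a reader might infer that the randomised controls let the trial answer the specialist-versus-general question free of confounding. The documents do not support that. Navigator type is not randomised in any analysis. The interaction shows whether the navigation effect differs by site type, and anything local that changes that effect stays mixed with navigator type. Its half-width of 21-28 points also exceeds the 20-point effect the trial targets.

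**Conclusion.** The point holds as a minor one. The planned comparison is restricted to the ONN arm, navigator type there is not randomised and largely follows the clinic, and a baseline site difference in OS6 or ACU would pass in full into the reported navigator difference. With no navigator-type effect, the chance of a significant OS6 result is about 8-10% for an assumed 5-point gap, 18-27% for 10 points and 52-78% for 20 points. For ACU, an assumed site rate ratio of 1.2 gives about 32-72%. These figures rest on the assumed splits, gaps and follow-up times. The existence of same-site controls is inferred from Sections 3.1 and 4.1. Because site is not a stratification factor, numbers per arm may be uneven within a site type, and the evaluable population in Section 11.4 adds selection after randomisation.

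Two stronger readings should be resisted. A reader might infer that the main results or a staffing decision are at risk. The co-primary tests do not use this contrast, and the policy aim in Section 1.2 concerns nurse navigation as a whole. A reader might also infer from Section 5 that only GI clinics enrol and the general-navigator group is empty. Section 3.1 recruits at LCI sites with the navigation program, so this is wording to reconcile, not evidence of an empty group.

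**What to change.** In Sections 2.1.3 and 11.5.7:

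1. Classify every analysed subject in both arms by the navigator type serving the enrolling site at randomisation (GI or general).
2. Report ONN versus control within each site type, with the numbers in each cell.
3. Report the arm-by-site-type interaction with its confidence interval on a named scale: risk difference for OS6, rate ratio for ACU.
4. Keep the within-ONN figures, labelled as descriptive and non-randomised.
5. State that the interaction removes the site main effect only, that site features which modify the navigation effect remain mixed with navigator type, and that precision is low.

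Separately, reconcile the description of subjects in Section 5 with the recruiting sites in Section 3.1.

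The cost is SAP wording, one site-type variable and its interaction with arm. The enrolling site should already be on record for each subject. The price is a standard error about 1.4 to 1.5 times that of the within-ONN contrast, so the result will seldom be decisive.

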11.5.8 Interim Analysis

After 100 subjects have been enrolled in the OS evaluable population, a formal interim analysis will be conducted. The interim analysis is designed primarily to assess futility regarding the 6-month OS rate objective and will be based on the conditional power. If the conditional power falls below 50%, the OS6 objective may be removed from the co-primary objective. If this occurs, the primary objective will be based only on the acute care utilization objective. With this revised design, 158 evaluable subjects would provide 90% power to detect a 20% reduction in acute care utilization from 6 visits per year in the non-navigation arm based on a 2-sided alpha = 0.05 significance level.

If the OS6 conditional power is greater than 50% but less than 80%, the sample size may be increased so that the power for the revised sample size is maintained at 80%. As discussed in Chen et al, 2004, this sample size re-estimation will not inflate the type I error.

Sample size re-estimation

As per protocol, the interim futility analysis occurred on 9/22/2022. Based on the results of the interim analysis and on the initial statistical design, the trial will proceed with OS6 and ACU as co-primary

endpoints. In order to retain 80% power for the OS6 objective, the sample size will be increased from 107 evaluable subjects per arm to 150 evaluable subjects per arm.

In order to achieve a total of 300 evaluable subjects, it is estimated that approximately a total of 347 subjects may be enrolled.

Additionally, ~~an~~ interim efficacy analysisanalyses will be performed after 85 and 120 deaths in the evaluable population have occurred (Interim Efficacy Analysis I and II). This will be conducted under the auspices of the LCI DSMC and will be blinded to the Sponsor-Investigator and the study conduct trial site. If, in the clinical judgement of the LCI DSMC, there are impelling favorable OS trends, the study may be terminated due to ethical considerations. No formal statistical stopping rules will be utilized, and no alpha spend will be incurred due to this interim efficacy evaluation.

As per protocol, Interim Efficacy Analysis I occurred on 1/23/2022. Based on the results of the blinded survival analysis and the updated statistical design (following the interim futility analysis on 9/22/2022), the trial will continue and Interim Efficacy Analysis II will be performed after 120 deaths in the evaluable population have occurred.

12. STUDY COMPLETION OR TERMINATION

12.1 Completion

The study will be considered complete when one or more of the following conditions is met:

- All subjects have withdrawn from the study
- All subjects have discontinued from the study
- The IRB, LCI DSMC, or Sponsor-Investigator discontinues the study because of safety considerations
- The Sponsor-Investigator defines an administrative or clinical cut-off date

12.2 Termination

The study will be terminated when one or more of the following conditions occur:

- If risk-benefit ratio becomes unacceptable owing to, for example,
 - Safety findings from this study
 - Results of parallel clinical studies
 - If the study conduct (e.g., recruitment rate, drop-out rate, data quality, protocol compliance) does not suggest a proper completion of the trial within a reasonable time frame
- The Sponsor-Investigator has decided to close the trial at any site and at any time

For any of the above closures, the following applies:

- Closures should occur only after consultation between involved parties.
- All affected institutions must be informed as applicable according to local law.

- In case of a partial study closure, ongoing subjects, including those in follow-up, must be taken care of in an ethical manner.

13. STUDY MANAGEMENT

13.1 IRB Approval

The study protocol, the informed consent(s) and any other necessary documents must be approved by the Sponsor IRB and site(s) IRB of record in accordance with federal regulations and obtained prior to implementation.

The Sponsor IRB and sites(s) IRB of record will be informed of any amendment to the protocol, informed consent(s), and any other necessary documents in accordance with IRB reporting requirements. The study protocol will undergo continuing IRB review based on the level of risk as assessed by the IRB no less than annually, or as applicable, in accordance with IRB requirements.

13.2 Informed Consent

Before recruitment and screening/enrollment onto this study, the subject will be given a full explanation of the study, the opportunity to review each consent form, and the opportunity to have all their questions answered. Prior to a subject's participation in the trial, the written informed consent(s) will be reviewed, signed and personally dated by the subject and by the person who conducted the informed consent discussion. Written informed consent may include electronic signatures when use of electronic informed consent is obtained from the subject on site or remotely. A copy of each informed consent will be given to the subject and each original will be placed in the subject's research record. An entry must also be made in the subject's dated source documents to confirm that informed consent was obtained prior to any study-related procedures and that the subject received a signed copy.

13.3 Protocol Adherence

Except for an emergency situation in which proper care for the protection, safety, and well-being of the study subject requires alternative treatment, the study shall be conducted exactly as described in the approved protocol.

13.3.1 Amendments to the Protocol and Informed Consent

If it is necessary for the study protocol to be amended and/or the informed consent revised, the amendment or a new version of the study protocol and/or revised informed consent must be approved by the Sponsor-Investigator and the Sponsor IRB.

13.4 Other Protocol Deviations

If a deviation occurs, the event should be reported promptly to the Sponsor-Investigator promptly. Any IRB reportable event that occurs must be reported to the IRB per IRB reporting requirements and to the Sponsor-Investigator as soon as possible but no later than 10 business days of awareness.

Protocol deviations that, in the Investigator's judgment, potentially caused harm to participants or others or indicates that the participants or others are at an increased risk of harm, or has adversely impacted data integrity will be reported promptly to the IRB per IRB reporting requirements.

Planned protocol deviations should be submitted to the Sponsor for approval prior to the anticipated deviation occurring. After Sponsor approval has been obtained, planned deviations should be submitted to the IRB prior to the anticipated deviation occurring. IRB approval must be obtained prior to deviation occurrence. No exceptions for eligibility criteria are not allowed.

13.5 Retention of Records

Essential documentation (e.g., source documents, Sponsor-Investigator correspondence, monitoring reports, and regulatory documents), including all IRB correspondence, will be retained for at least 2 years after the investigation is completed. Documentation will be readily available upon request.

13.6 Ethical and Legal Conduct of the Study

The procedures set out in this protocol, pertaining to the conduct, evaluation, and documentation of this study, are designed to ensure that the Investigator abide by GCP guidelines. The study will also be carried out in full conformity with Regulations for the Protection of Human Subjects of Research codified in the ICH E6 and in keeping with applicable local law(s) and regulation(s).

Documented approval from appropriate agencies will be obtained for all participating centers before the start of the study, according to GCP, local laws, regulations and organizations.

Strict adherence to this protocol is required for all aspects of study conduct; the investigators may not modify or alter the procedures described in this protocol.

The Sponsor-Investigator is responsible for the conduct of the trial at the sites in accordance with the Declaration of Helsinki. The Sponsor-Investigator is responsible for overseeing all study subjects. The Sponsor-Investigator must assure that all study site personnel, including sub-investigators and other study staff members, adhere to the study protocol and all applicable regulations and guidelines regarding clinical trials both during and after study completion.

The Sponsor-Investigator will be responsible for assuring that all the required data will be collected and properly documented.

